**General information**

Please provide information for all items marked "M" (mandatory).

Items marked "O" are optional.

M	Investigator/institution and contact person: [name] Institut Bergonié, Bordeaux, France	
M	IIR Subtype	Non-interventional/Observational
M	Study Title (Full)  A retrospective Study to Determine the Treatment Outcomes of Subjects with Locally advanced/unresectable or Metastatic Solid Tumors with NTRK Fusions	
M	Indication: Solid Tumors	
M	Phase of Study	Observational
M	Country	France
M	Retrospective or prospective study	Retrospective
M	Planned number of sites/ subjects	3750 subjects (up to 10 sites)
M	Blinding & Control	n/a

**Additional request details**

M	Primary Endpoint/ objective is safety	No
M	Study exploring new combinations, alternative dosing/dosing schedules or new formulations	No

M	Study with clinical pharmacology objectives, including biomarker, pharmacokinetic (PK) or pharmacodynamics (PD) evaluations	No
O	Author	[name], PhD Institut Bergonie Early Phase Trials and Sarcoma Units [name] Phone: [name] Fax: [name] E-mail: [contact]
O	Investigator Operations Manager email	[name], PhD  Head of Clinical Research Unit: [name] Institut Bergonié – Bordeaux Phone :[name] E-mail : [contact]
M	Study support	Financial
M	Study is financially supported by other organizations	No

Rationale and objectives	
O	Please explain why this study is non-blinded (if applicable): This is a retrospective study.
M	Study Type and Design  This multicenter, retrospective study has a primary objective to assess the impact of NTRK gene fusions on the PFS of first-line systemic therapy for the treatment of locally advanced/unresectable or metastatic solid tumors.  Control subjects will be matched based on the characteristics of the NTRK fusion study population to the greatest extent possible.
M	Rationale  The tropomyosin receptor kinase (Trk) receptor family comprises 3 transmembrane proteins referred to as Trk A, B and C (TrkA, TrkB and TrkC) receptors that are encoded by the NTRK1, NTRK2 and NTRK3 genes, respectively. These receptor tyrosine kinases are expressed in human neuronal tissue and play an essential role in the physiology of development and function of the nervous system through activation by neurotrophins. Gene fusions involving NTRK genes lead to transcription of chimeric Trk proteins with constitutively activated or overexpressed kinase function conferring oncogenic potential. These genetic abnormalities have recently emerged as targets for cancer therapy, because novel compounds have been developed that are selective inhibitors of the constitutively active rearranged proteins. Developments in this field are being aided by next generation sequencing methods as tools for unbiased gene fusions discovery. However, the incidence

	of NTRK aberrations in solid tumors is unknown as well as the natural history of NTRK-rearranged tumors.
M	
Primary Study Objective
 
To assess retrospectively the effect of NTRK gene fusions on the progression free survival (PFS) of first-line systemic therapy for the treatment of locally advanced/unresectable or metastatic solid tumors

O	
Secondary Study Objectives
 
 
• To evaluate the frequency of NTRK gene fusions in subjects with locally advanced/unresectable or metastatic solid tumors.
 
• To assess the treatment outcome to first-line anti-cancer therapy in terms of objective response rate (ORR), duration of response (DOR), and overall survival (OS) in subjects with locally advanced/unresectable or metastatic solid tumors with NTRK gene fusions.
 
• To explore possible demographic characteristics prevalent in subjects with locally advanced/unresectable or metastatic solid tumors and NTRK gene fusions.
 
• To explore the frequency and treatment outcome interaction of concomitant genetic alterations.
 
• To look for trends in the data that may suggest relationships between covariates of interest and treatment outcome in subjects with locally advanced/unresectable or metastatic solid tumors harboring NTRK gene fusions.
 

M	
Study operational/organizational aspects
 
This will be a multicenter, retrospective study. Institut Bergonié as the Sponsor of this study, will be responsible for getting regulatory approvals, selecting the investigational sites, capturing study data in an appropriate data base

Population and methods	
M	
Study Population
 
Adult and pediatric patients with locally advanced/unresectable or metastatic solid tumors

M	
Inclusion Criteria (detailed)
 
For inclusion of a subject in the study population, all of the following criteria must be fulfilled:
 
 
1. Age <math>\geq</math> 1 month.
 

2. Subject has/had a histologically or cytologically confirmed diagnosis of solid tumor including but not exclusively: soft tissue sarcoma, BRAF wild type melanoma, KRAS wild-type colorectal cancer, central nervous system, EGFR-wild type non-small cell lung cancer.

3. Subject has locally advanced/unresectable or metastatic disease.

4. Subject has received at least one systemic anti-cancer therapy for locally advanced/unresectable or metastatic disease for which there is available outcome information in terms of PFS, or the latter can be estimated based on the subject's records.

5. Subject has tumor material available for immunoscreening (IHC for NTRK gene fusions).

6. Written and voluntary informed consent understood, signed and dated, or a waiver of consent is granted according to French regulations

Subjects who are tested positive by IHC (Pan-Trk IHC testing with mAb EPR17341) will be the subject of molecular assays such as next-generation sequencing (Archer Dx fusion assay) of tumor material [parrafin embedded material]), so that tumor harboring *NTRK1*, *NTRK2* or *NTRK3* gene fusions, is identified properly.

After identification of the NTRK fusion study population, control subjects with locally advanced/unresectable or metastatic solid tumors, who do not have NTRK fusions will be selected in an attempt to closely match NTRK fusion subjects.

M	
Exclusion Criteria
 
The following exclusion criterion should be considered:
 
Subjects who have not yet received or completed at least one systemic anti-cancer therapy for locally advanced/unresectable or metastatic cancer.

M	
Test Treatment(s) (Description)
 
n/a
 
.

O	
Test Treatment(s) or Investigated Treatment(s): Rationale for unusual or novel approaches
 
n/a

M	
Request for Study Drug Supply
 
No

M	
Reference Treatment or Modality/Treatment or Modality of Comparison (Description)

	n/a
--	-----

Safety reporting	
M	Safety reporting (valid for clinical studies only) n/a

Statistical analysis	
O/M	Standard of Reference/Standard of Truth n/a
M	Rationale for selection of a reference treatment n/a
M	Assignment of subjects to study arms or groups (Randomization/Stratification) n/a (this will be a retrospective study)
M	Blinding n/a
M	Concomitant Treatment(s) n/a
M	Primary Outcome Progression-free survival observed with first-line anti-cancer therapy
O	Secondary Outcomes 
 
Frequency of NTRK fusions in subjects with locally advanced/unresectable or metastatic solid tumors.
 
Treatment outcome to first-line anti-cancer therapy in terms of objective response rate (ORR), duration of response (DOR), and overall survival (OS) in subjects with locally advanced/unresectable or metastatic HNSCC with NTRK gene fusions.
 
Demographic characteristics in subjects with locally advanced/unresectable or metastatic solid tumors harboring NTRK gene fusions
 

M	Safety Outcomes n/a
O	Measurement of results (How assessed)

	Data collection (see below)		
M	Visit schedule		
	Activity	Screening	Data Collection for Enrolled Subjects
	ICF, Inclusion/exclusion criteria evaluation	X	
	Collection of Demographic Information: 
 
• Date of birth
 
• Vital status: dead/alive/unknown
 
• Gender
 
• Smoking status: Smoker/never smoker/prior smoker at the time of first line treatment
 
• Other relevant carcinogen exposure (e.g. consumption of betel nut)
 
		X
	Collection of Medical Information: 
 
• Date of initial diagnosis of cancer
 
• Stage of disease at diagnosis
 
• Anatomical disease site(s) at diagnosis
 
• Anatomical (organ) disease site(s) (e.g. lung metastases) at the time of first line treatment
 
• Locally advanced/unresectable or metastatic disease at the time of first line treatment
 
• Current stage of disease
 
• Other relevant medical history. Date of prior medical events
 
		X
	Collection of Treatment Information: 
 
• Prior/current surgical treatments for cancer. 
 
• Dates of surgeries
 
 
 
• Prior/current radiological treatments for cancer. 
 
• Anatomical sites.
 
• Dates of radiation treatments
 
 
 
• First line systemic treatment for locally advanced/unresectable or metastatic cancer: 
 
• Dates of treatment (start, end).
 
• Performance status at the time of first line therapy for treatment of recurrent or metastatic disease.
 
• Treatment outcome (response and response criteria).
 
• Date of progression(s) (progression criteria).
 
 
 
• Other prior/current systemic treatments for cancer. 
 
• Dates of treatment (start, end).
 
• Treatment outcome (response and response criteria).
 
 
 
• Date of progression(s) (progression
 
		X

	
criteria)
 
 
• Date of death (if any) and cause of death
 
 
Collection of NTRK fusion Information:
 
 
• Anatomical biopsy sample site (including blood/urine sample). Date of sampling and setting (initial diagnosis, locally advanced/unresectable or metastatic disease)
 
• Matrix (tumor biopsy, blood, urine)
 
• Tumor histology (from biopsy sample or primary diagnosis)
 
• NTRK fusion in sample. Allele frequency (if available); this information is not applicable for control subjects.
 
• Other relevant mutations or genetic alterations, if available. Allele frequencies (if available)
 
• Test platform (e.g. NGS). Mutations tested (PCR methods) or exons sequenced (sequencing methods).
 
		
			X
M	
Follow-up period
 
n/a
		
M	
Statistical & Analytical Plan and Methodology
 
The primary objective of this descriptive study is to determine if there are statistically significant differences in PFS to first line systemic therapy between subjects with recurrent/metastatic disease and NTRK fusion versus those without a known NTRK fusion.
 
The two groups will be matched with respect to histological subtype, sex, age (+/-5 years), and pathological tumor-node-metastasis (TNM) stage.
 
The Kaplan-Meier method will be employed for the analysis of PFS. A nonparametric test, such as the log-rank test, based on the Kaplan-Meier estimator for survival curves, will be employed to assess the association between PFS and the presence of NTRK fusion. In addition, predictive modeling, including Cox proportional hazards models with NTRK fusion as a predictor may also be used to estimate the relative risk of the exit-event of subjects with tumors with NTRK fusion versus subjects with tumors without known NTRK fusion. If the data allow it, other types of predictive modeling may also be explored. If the proportionality of hazard assumption fails, then parametric approaches will be used.
		

	
Given the rarity of NTRK fusions among subjects with solid tumors, the sample size for this study will not be driven by powering the study. A post hoc power calculation will be provided. Clinically relevant changes will be defined as increases in median survival times that are greater than 30%, regardless of confidence interval width.
 
An assessment of the impact of certain covariates will be conducted by comparing their associated hazard ratios from the Cox proportional hazard (or parametric model) analysis.
 
Descriptive statistics will be employed to define demographic and treatment outcome, as well as overall frequency of NTRK fusions in the screened population. This will include exploration of potential effects on subject's treatment outcomes of different forms of NTRK fusions and of other genetic alterations.

--	--

Timelines	
M	
Planned Study Timelines:
 
 
1. Enrolment rate (patients per month): 300 patients/months
 
2. Planned estimate of treatment duration: not applicable
 
3. Submission date to health authority/ethics: not applicable
 
4. Start of subject enrolment: December 2018
 
5. End of Subject enrolment: December 2019
 
6. All patients completed: December 2019
 
7. End of Study: March 2020
 
8. Report (as described in the contract): Report every 3 months
 
9. Planned publication/presentation: June 2020
 

Limitations	
O	
Criteria for selection of evaluable cases:
 
All patients:
 
who have received at least one systemic anti-cancer therapy for locally advanced/unresectable or metastatic disease for which there is available outcome information in terms of PFS,
 
who have tumor material tested by IHC for NTRK gene fusions,
 
will be included in the analysis.

M	Interim Analyses (if applicable)

	
Interim analyses will be the subject of periodic reports based upon collection of data on first 1,000, 2,000 patients and a final analysis will be conducted after completion of the whole data set analysis.
 
At each interim analyses, the proportion of NTRK-rearranged cases will be estimated in order to assess the feasibility of a comparative analysis with matched controls.

M	
Number of Evaluable Patients (estimate): it is anticipated to collect data on 3,700 patients

M	
Sample Size Assumptions/Target Number of Valid Cases (incl. Power and Confidence)
 
No sample size estimate has been calculated. It is assumed that a sample size of 3,700 patients should be sufficient to address the primary objective of this study.

0	
Statistical analyses
 
 
Quantitative variables will be described using mean and standard deviations if the normality assumption is satisfied, else other descriptive statistics (median, range, quartiles) will be reported.
 
Qualitative variables will be described using frequency, percentage and 95% confidence interval (binomial law).
 
Survival endpoints will be analysed using the Kaplan-Meier method. The median survival rates will be reported with a 95% confidence interval. Median follow-up will be calculated using the reverse Kaplan-Meier method.
 

M	
Health Economic Variables (if applicable)
 
n/a

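### The first-line agent is not listed for collection, matched or stratified on, so any first-line TRK-inhibitor use could appear as an effect of the NTRK fusion on PFS; its extent is unknown and may be small.

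*Combined protocol and SAP*

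**What the plan says.** All references are to the combined protocol and SAP.

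- **Rationale.** It says that "novel compounds have been developed that are selective inhibitors of the constitutively active rearranged proteins". It also says that the incidence "of NTRK aberrations in solid tumors is unknown as well as the natural history of NTRK-rearranged tumors".
- **Primary Study Objective.** "To assess retrospectively the effect of NTRK gene fusions on the progression free survival (PFS) of first-line systemic therapy". The Primary Outcome is "Progression-free survival observed with first-line anti-cancer therapy". Neither names or removes a drug class.
- **Inclusion Criteria.** "Subject has received at least one systemic anti-cancer therapy for locally advanced/unresectable or metastatic disease", with PFS known or estimable. The Exclusion Criteria contain one entry: "Subjects who have not yet received or completed at least one systemic anti-cancer therapy for locally advanced/unresectable or metastatic cancer". The rule for evaluable cases adds no restriction on treatment.
- **Visit schedule, treatment information.** Under "First line systemic treatment for locally advanced/unresectable or metastatic cancer" the listed items are treatment dates, performance status, response and progression. Agent, regimen and class are not listed. The entry for other systemic treatments does not list them either.
- **Statistical & Analytical Plan and Methodology.** "The two groups will be matched with respect to histological subtype, sex, age (+/-5 years), and pathological tumor-node-metastasis (TNM) stage". The log-rank test has no treatment stratum. The Cox model is optional, with fusion as its only named predictor, and the further covariates are not named. An increase in median of more than 30% counts as clinically relevant whatever the width of the confidence interval.
- **Planned Study Timelines.** Enrolment starts in December 2018. No section limits when first-line therapy was given.

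**The concern.** A drug directed at the fusion protein would be given to patients known to carry the fusion and, in practice, not to controls. If some fusion patients received one first-line, the fusion group's PFS combines any effect of the fusion with the effect of that drug. A longer PFS could then be credited to the fusion, or a harmful effect of the fusion could be hidden.

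None of the four matching factors bears on this, because two patients of the same histology, sex, age and stage can still have received different first-line drugs. With no agent or class among the listed items, the final report might be unable to show how many patients were affected, or that none were.

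The same gap covers conventional regimens: the groups could differ in first-line class for reasons unrelated to TRK inhibitors, and the plan would not show it.

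**Working it through.** The plan states no power, effect size, event count or sample-size calculation, so there is no figure to reproduce. The first step is to read the sections against each other; the second is to illustrate the possible size.

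**Step 1. Where could the plan have dealt with first-line agent?**

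| Section | Treatment restriction or use |
|---|---|
| Inclusion, exclusion, evaluable cases | None; any systemic therapy qualifies |
| First-line data items | Agent and class not listed |
| Matching | Four factors; treatment is not one |
| Log-rank test | Not stratified by treatment |
| Cox model | Optional; fusion is the only named predictor |

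The gap is present in each place.

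**Step 2. How large could the effect be?** The 30% threshold is the plan's, read here as applying to median PFS. Everything else is assumed: the fusion has no effect, PFS is exponential, a share f of fusion patients received a first-line TRK inhibitor, and the drug multiplies median PFS by R. With time t in units of the control median, PFS in the fusion group is

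S(t) = (1 − f) × 0.5^t + f × 0.5^(t/R).

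Setting S(1.3) = 0.5 gives the share that alone raises the median by 30%:

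f = (0.5 − 0.5^1.3) / (0.5^(1.3/R) − 0.5^1.3), where 0.5^1.3 = 0.4061 and the numerator is 0.0939.

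| R | 0.5^(1.3/R) | f that reaches 30% | Median increase at f = 10% | at f = 20% | at f = 30% |
|---|---|---|---|---|---|
| 2 | 0.6373 | 0.0939/0.2312 = 41% | 6% | 13% | 21% |
| 3 | 0.7405 | 0.0939/0.3344 = 28% | 9% | 20% | 33% |
| 4 | 0.7983 | 0.0939/0.3922 = 24% | 11% | 24% | 40% |
| 5 | 0.8351 | 0.0939/0.4290 = 22% | 12% | 27% | 46% |
| 6 | 0.8606 | 0.0939/0.4545 = 21% | 13% | 29% | 50% |

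The last three columns solve S(t) = 0.5 for t. The matching large-sample Cox hazard ratios (1:1 groups, full follow-up) at f = 10%, 20% and 30% are 0.92, 0.85 and 0.79 for R = 2; 0.86, 0.76 and 0.68 for R = 3; and 0.81, 0.69 and 0.59 for R = 5. With f = 0 both the median ratio and the hazard ratio are 1.00.

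**Step 3. What would this mean in patients?** The documents give no fusion frequency. At assumed values of 0.2%, 0.3%, 0.5% and 1%, 3,700 patients yield about 7, 11, 18 and 37 fusion cases. Taking 11, the same model with R from 3 to 6 gives a median increase of 8% to 11% if one patient was treated, 18% to 26% if two, and 29% to 44% if three. These are large-sample medians applied to a very small group. In a simulation of 11 against 11 with no censoring, no fusion effect and no TRK inhibitor, the observed median ratio exceeded 1.3 in 33% of studies.

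**The case against.** The strongest reply is that exposure is undocumented and probably low. No section says that any patient received such a drug first-line. The Rationale presents the compounds as new, and the study establishes fusion status itself, by IHC followed by sequencing, in patients who had already had first-line therapy. First-line use would have needed fusion testing outside the study before treatment. The exclusion of patients who have not completed a therapy may also remove some still on a long-lasting inhibitor. All of this stands, and it limits how large the problem is likely to be. It does not rule exposure out, and the listed data items would not let the sponsor show that exposure was negligible.

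A second reply is that receiving a fusion-directed drug is a consequence of a known fusion. Leaving it in could then be legitimate if the target is PFS under whatever therapy was given. That is fair: the objective does not say which is meant. Both comparisons can be reported, but the plan must say which is primary, and neither can be separated out without the agent.

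A third is that the heading for first-line treatment might be taken to imply recording the drug. The items beneath it do not say so.

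Finally, crossing the 30% threshold in groups of about 11 is weak evidence of anything, as the 33% chance figure shows. This stands too. The illustration shows how far drug use could move the expected result; it does not mean that an observed increase of 30% would point to the drug.

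**Conclusion.** The gap is certain; its size cannot be determined from the documents. Followed as written, the plan could attribute a drug effect to the fusion, and no listed item would reveal it. Under the stated assumptions, reaching 30% by this route alone needs 41% of fusion patients treated if the drug doubles median PFS and 21% if it multiplies it by six. At a share of 10% the shift is about 6% to 12% for 2- to 5-fold gains (13% at 6-fold), and it is smaller at lower shares. It is worth correcting because the correction is cheap.

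Three stronger readings are tempting and not supported.

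- **That drug and fusion are fully confounded.** This would require nearly all fusion patients to have had an inhibitor first-line. At the shares considered here most had conventional therapy, and exclusion separates the two effects.
- **That the study's stated aim is natural history or prognosis.** Natural history appears in the Rationale as something unknown; it is not among the objectives or outcomes.
- **That OS is biased in the same way.** The secondary objective and outcome describe OS only in subjects with fusions, with no comparison against controls. Later-line inhibitors call for a caveat on that description, and no more.

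**What to change.** 1. **Data items.** Add the first-line agent or class, and any later-line TRK-inhibitor use, to the treatment information in the Visit schedule.
2. **Primary PFS comparison.** Exclude patients whose first-line therapy was a TRK inhibitor, together with their matched controls. Describe the excluded fusion patients separately, and report the all-patient comparison as a sensitivity analysis. If there are none, the report can say so.
3. **Other first-line classes.** Report their distribution by group, and match on or adjust for class where both groups overlap. Matching or Cox adjustment cannot deal with TRK-inhibitor class itself, because exposure lies on one side only.
4. **OS.** State how many fusion subjects received a TRK inhibitor in any line, and describe OS separately for them as a caveat. Do not rely on censoring at inhibitor start: patients who start one in a later line have typically progressed, so that censoring would be informative.

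The cost is one more data item, a few lines of analysis text and possibly the loss of a few fusion patients from an already small primary comparison. The number lost should be reported. Patient care does not change.

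### ORR, DOR and OS are planned in fusion patients only, so a result pooled over many histologies has no stated reference, although matched controls are planned for PFS

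*Combined protocol and SAP*

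**What the plan says.** All references are to the combined protocol and SAP.

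- **Secondary Study Objectives.** The objective is "To assess the treatment outcome to first-line anti-cancer therapy in terms of objective response rate (ORR), duration of response (DOR), and overall survival (OS"), and it continues "in subjects with locally advanced/unresectable or metastatic solid tumors with NTRK gene fusions".
- **Secondary Outcomes.** The same three endpoints are listed, again for fusion patients only, but here "in subjects with locally advanced/unresectable or metastatic HNSCC with NTRK gene fusions".
- **Inclusion Criteria.** Any solid tumour type may enter; sarcoma, melanoma, colorectal, CNS and lung tumours are named as examples. Adults and children are both eligible.
- **Statistical & Analytical Plan and Methodology.** The comparative aim concerns first-line PFS alone, in fusion patients against patients with no known fusion. The groups are matched on histological subtype, sex, age within 5 years and TNM stage. A log-rank-type test "will be employed to assess the association between PFS and the presence of NTRK fusion". Other treatment outcomes come under descriptive statistics, with no control group mentioned.
- **Visit schedule.** The items listed for enrolled subjects include vital status, "Treatment outcome (response and response criteria"), progression dates and "Date of death (if any) and cause of death". Only the fusion and allele-frequency item is marked as not applying to controls.
- **Interim Analyses.** The proportion of fusion cases is estimated at each interim look, to judge whether a matched comparison is feasible.

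**The concern.** The plan accepts that PFS in fusion patients needs controls of the same histology, sex, age and stage before it can be read. ORR and OS in the same patients raise the same difficulty, yet no reference is planned for them. First-line response and survival differ between tumour types, so a pooled figure depends heavily on which histologies happen to be among the fusion cases.

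A reader given a fusion-only ORR or median OS could not tell whether it reflects the fusion or the tumour mix. If a control comparison were added after the results were seen, the endpoint, the effect measure and the handling of matching would all be chosen with knowledge of the data.

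**Working it through.** The plan states no sample size derivation, power or event count for these endpoints, so there is no figure to reproduce. The check is a reading of the text followed by two illustrations.

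**1. Does any section plan ORR, DOR or OS in controls?**
- The objective and the outcome list both restrict these endpoints to fusion patients.
- The methodology section sets out matching and the log-rank-type test for PFS. The Cox model follows for an exit event and names no other endpoint.
- The same section defines a relevant change through median survival times and names no endpoint.
- The later Statistical analyses list applies Kaplan-Meier to survival endpoints and names no groups.

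None of these commits to a control summary of ORR, DOR or OS.

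**2. Would the data exist?**
- *ORR:* response and response criteria are listed.
- *OS:* vital status and date of death are listed, but no date of last contact, which is needed to censor patients still alive.
- *DOR:* progression dates are listed, but no date of first response.
- The form appears to cover controls, because a single item is marked as not applying to them.

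**3. Effect of case mix on a fusion-only ORR.** Assume two histologies with ORRs of 10% and 50% and no fusion effect. With w the share of the more responsive one, expected ORR = 10% × (1 − w) + 50% × w.
- w = 20%: 8% + 10% = 18%
- w = 50%: 5% + 25% = 30%
- w = 80%: 2% + 40% = 42%

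Controls with the same w have the same expected ORR, so the expected difference is zero. If matching is incomplete, the difference that remains is 40 points (50 − 10) times the difference in w between the groups.

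**4. Precision.** The rationale calls the frequency of NTRK aberrations unknown. Assumed frequencies of 0.2%, 0.3%, 0.5% and 1% of 3,700 give 7.4, 11.1, 18.5 and 37, or about 7, 11, 19 and 37 cases. The matching ratio k is not stated, so 1:1 and 4:1 (controls to cases) are shown. ORR is taken near 30% in both groups. The half-width of the 95% CI for the ORR difference is 1.96 × √[p(1 − p)(1/n + 1/(kn))], which ignores the matching.

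| Fusion cases | Fusion-only ORR, exact 95% CI | Half-width, 1:1 | Half-width, 4:1 |
|---|---|---|---|
| 7 | 2/7: 4% to 71% | 47.3 points | 37.4 points |
| 11 | 3/11: 6% to 61% | 37.2 points | 29.4 points |
| 19 | 6/19: 13% to 57% | 29.6 points | 23.4 points |
| 37 | 11/37: 16% to 47% | 20.8 points | 16.5 points |

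For OS, take a 30% longer median (HR 1/1.3, exponential), two-sided alpha 0.05 and an event in every patient. Power is then 7% to 20% at 1:1 and 9% to 30% at 4:1 over the same range of cases. About 457 events (Schoenfeld) would be needed for 80% power at 1:1. These comparisons can only be estimates with intervals.

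**5. Choice of measure for ORR.** With 1:1 pairs and 30% ORR in both groups, independent within pairs, the expected number of discordant pairs is n × 2 × 0.3 × 0.7 = 0.42n. For 11 pairs that is 4.6, too few for a usable conditional odds ratio.

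**The case against.** The strongest reply is that these endpoints are meant to be descriptive. The study title and the secondary objective concern outcomes in fusion patients, the section is marked optional, and the comparative question is assigned to PFS. A reader might infer that the rationale promises to show whether the fusion changes response or survival. It does not: it says that the natural history of these tumours is unknown, and describing the fusion group answers that. This stands, and it is why the added figures should also be descriptive.

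The unassigned wording on survival endpoints and median survival times does not exclude control summaries. That also stands, but permission is not a plan, and the two sections that name the endpoints restrict them.

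Sampling error is a fair objection too. In 11 patients the standard error of a 30% ORR is √(0.3 × 0.7/11), about 14 points, against a case-mix swing of 12 points either side of 30%. More cases would shrink the first but would not supply a reference for the second.

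Two further inferences go too far. One is that the comparison needs only extra analyses of data already held: the data are planned, and two dates are missing from the form. The other is that matching removes case mix entirely: the plan describes matching as best effort, and first-line regimen is not a matching factor.

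**Conclusion.** The point holds as a limited one. ORR, DOR and OS are restricted to fusion patients in both places that define them, and no section commits to the same outcomes in the matched controls. Under the assumed ORRs of 10% and 50%, tumour mix alone moves the expected fusion-only ORR between 18% and 42%. That range depends on the assumed rates and shares, but not on the number of fusion cases.

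The mixed-histology premise follows the objective. If HNSCC in the outcome list were intended, histology would be far less mixed, but there would still be no control reference.

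The documents do not support reading this as a flaw in the primary analysis, or as a case for powered tests of ORR or OS. It is a cheap improvement that makes secondary results easier to interpret.

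**What to change.** If the feasibility check allows the matched PFS comparison, report the secondary outcomes in the same matched controls, labelled descriptive and specified before outcome data are examined:

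- **ORR:** both proportions and a risk difference with a 95% CI that respects the matching, in preference to a conditional odds ratio.
- **OS:** Kaplan-Meier curves by group and a hazard ratio with a 95% CI that accounts for the matched sets.
- **DOR:** description only, in responders of both groups, because it is conditional on response.
- **Data form:** add date of first response and date of last contact for both groups. The second is also needed for the reverse Kaplan-Meier follow-up already planned.
- **Text:** reconcile HNSCC in Secondary Outcomes with solid tumors in Secondary Study Objectives.

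The cost is two data fields with their chart abstraction, and a few analyses on a control group that is being selected anyway. Intervals will be wide. Differences in first-line regimen and in later-line treatment will remain and should be stated as caveats beside the results.
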